We will power the study to detect a 250mL difference in calculated intra-operative blood loss between groups. This effect size has been used in the total hip literature, and it is considered to be a clinically significant difference in blood loss¹⁵. Our analysis shows that 12 patients are required in each arm of the study (24 patients total) to achieve 81% power with an independent-sample t-test and statistical significance set to alpha equal to 0.05. Expecting that 10-25% of patients will be excluded, we will aim to enroll a total of 30 patients in this study.

Patients aged 18 or younger will be screened for study eligibility

3. Interventions or Observations – what data are going to be collected and from what source?

Only anesthesiologists agreeing to participate in the study will be paired with the study surgeons. Anesthesia will be conducted in a standardized fashion. The anesthesiologist will perform a neuraxial block (epidural, spinal, combined-spinal epidural) as well as administer general anesthesia. A neuraxial block will be placed using bupivicaine. A balanced general anesthetic utilizing a combination of either isoflurane, sevoflurane with or without nitrous oxide, vecuronium, midazalam and either fentanyl, morphine or dilaudid as the narcotic will be used at the discretion of the anesthesiologist. If a combined-spinal epidural is unsuccessful and an epidural and/or spinal are successfully obtained, the patient will still be included in the study. Patients not receiving neuraxial anesthesia will be excluded from the study. Arterial and venous access will be obtained in the usual sterile manner for monitoring.

The blood pressure target will be 20-25% below baseline, which will be achieved primarily with the combination of the general anesthesia and the neuraxial anesthesia. For blood pressure above this range, the epidural will be dosed with a short-acting local anesthetic, and/or the depth of the general anesthetic and will be titrated as per the anesthesiologist's judgment. For hypotension below this range, intravenous pressors, crystalloid, colloid or blood will be given. The technique of induced hypotension will not be utilized during these cases. Additional maintenance IV fluids or colloid will be given to maintain urine output of at least 0.5-1ml/kg/hr. Toradol and IV acetaminophen may be given towards the end of the case per the anesthesiologist's discretion.

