Attending surgeons, orthopedic surgery residents, physician assistants and research assistants involved with this study will assist in data collection. For each patient, we will collect demographic data, pre-operative CBC data, intra-operative cell saver auto-transfusion volumes, post-operative number of packed red blood cell units transfused, post-operative CBC data, post-operative drain outputs, and post-operative complications. This information will be gathered from the peri-operative medical records and electronic medical records.

A sticker will be place on the front of each participating patient's chart identifying him or her as a study patient. Their enrollment will also be communicated in the clinician rounding notes for each patient. Drains will be labeled for each study participant as well, and nurses will record the drain outputs per their floor protocol.

Data recorded from the electronic medical record will include:

- Date of surgery
- Patient age at the time of surgery
- Patient sex
- Patient height (cm) and weight (kg) at time of admission
- Preoperative CBC data and coagulation study data

- Postoperative hemoglobin on all inpatient days postoperatively (g/dL)
- Transfusion requirement during inpatient stay (units required)
- Transfusion reaction
- Total 24-hour drain output
- Postoperative day and time of discharge
- Chart review of progress notes for evidence of clinically significant VTE
- Chart review of progress notes for evidence of reoperation, hematoma, seroma, or postoperative infection

Data recorded from the operating room record will include:

- Anesthetic used (e.g., spinal/epidural, general, etc.)
- Operative times (minutes)
- Intra-operative transfusion requirements (units of blood)
- Use of cell saver intraoperatively (auto-transfusion volume, mL)
- Intra-operative complications

Data recorded from outpatient postoperative office records will include:

- Chart review of progress notes for evidence of clinically significant VTE through six weeks post-operatively
- Chart review of progress notes for evidence of re-operation, hematoma, seroma, or postoperative infection through six weeks post-operatively

Patients will be randomized to either the intervention or control group, as per randomization protocol described elsewhere in the proposal. For patients who are randomized to the control group, study data will be collected in the same manner as for the intervention group.

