VTE prophylaxis is not commonly used for pediatric patients at our institution. However, all patients will also receive a comprehensive approach to postoperative care comprised of mechanical (sequential compressive device) prophylaxis in-house, early mobilization with physical therapy, medical optimization, and regional anesthesia (if appropriate).

4. What is the long-term significance?

There are certain risks associated with blood loss and blood transfusion after elective orthopaedic procedures in young patients. Blood loss and transfusion requirements can be reduced with several blood conservation measures, including the use of pharmacological agents such as EACA. If the use of IV EACA is shown to decrease blood loss and transfusion requirements after bilateral VROs, it will provide an efficacious and inexpensive method to reduce post-operative morbidity and improve patient outcomes after bilateral VROs.

D. SAMPLE SIZE AND DATA ANALYSIS

Sample Size -

- 1. Proposed analysis (e.g., student's t-test, ANOVA, chi-square, regression, etc.): Independent samples t-test will be utilized if the data is normally distributed (or non-parametric Mann-Whitney U test if assumption of normality is not met).
- 2. Alpha level: 0.05
- 3. Beta or power level: 0.81
- 4. Primary outcome variable estimate (mean +/- s.d. for continuous outcome, frequency/percentage for categorical variable):

The primary outcome of interest in total intra-operative blood loss, which will be summarized as mean +/- standard deviation. Based on an analysis of the twenty-four consecutive cases of bilateral VROs, the mean calculated intra-operative blood loss was 671.24mL (SD: 233.69).

- 5. Number of groups being compared (use 1 for paired analysis within the same subjects): Two groups are being compared: Treatment Group (Loading Dose + Infusion) vs. Placebo Group (NS)
 - 6. Effect size or change expected between groups: 250cc

- 7. Resulting number per group: 12
- 8. Total sample size required: 24

Data Analysis

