The primary outcome of interest (calculated total blood loss) will be presented as a mean +/-standard deviation and compared between the EACA and placebo groups with a two-sample t-test. Multivariable linear regression models will also be used to adjust for any potential confounding due to total blood loss volume between arms after adjustment for age, sex, BMI, and anesthesia type. To adjust for any patients lost due to early withdrawal, we will increase our sample size by 3 patients in each group for a total sample size of 30 patients.

Calculated total blood loss will be determined from the difference between the preoperative hemoglobin and the postoperative hemoglobin (or the lowest postoperative hemoglobin during the hospital stay prior to transfusion). Based on hemoglobin balance, the estimated blood loss will be calculated according to the formula by Nadler et al.¹⁷:

```
Estimated Blood Volume (EBV) = (k_1 \text{ x Height}^3 \text{ (m)}) + (k_2 \text{ x Weight (kg)}) + k_3
For men, k_1 = 0.3669, k_2 = 0.03219, and k_3 = 0.6041
For women, k_1 = 0.3561, k_2 = 0.03308, and k_3 = 0.1833
```

Multiplying the EBV by the hematocrit (Hct) gives the red blood cell (RBC) volume. As such, a change in the RBC volume can be calculated from a change in the Hct level^{23,24}:

```
Total RBC volume loss = EBV \times (Hct Preop - Hct Postop)
```

Transfusions (mean volume per unit at HSS, 250 mL) can be taken into account by calculating the total blood loss¹⁶:

Total blood loss (L) = Total RBC volume loss + (No. of Units Transfused x 0.25) / (Hct Preop – Hct Postop) / 2)

All continuous secondary outcomes such as postoperative allogeneic blood transfusion requirement, intraoperative cell saver utilization, and length of hospital stay, will be analyzed in the same manner as the primary outcome.

Complications will be reported as incidence rates with 95% confidence intervals.

All hypotheses will be evaluated with two-sided tests with statistical significance set at $\alpha = 0.05$.

Bibliography

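### The primary test compares absolute mL of blood loss in patients of any size up to age 18 with no adjustment for body size, although the plan's formula scales red-cell loss with blood volume

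*Combined protocol and SAP*

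**What the plan says.** All references are to the combined protocol and SAP.

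- **Endpoint and test.** Under Data Analysis in section D, the plan states: "The primary outcome of interest (calculated total blood loss) will be presented as a mean +/-standard deviation and compared between the EACA and placebo groups". The method named there is the t-test for two independent samples. The Sample Size list in section D allows a Mann-Whitney test if normality fails. Neither test uses a covariate.
- **Formula.** Outcome Measures and Data Analysis give EBV as a function of height cubed, weight and sex. Red-cell volume loss is EBV times the fall in hematocrit. A transfusion term is then added.
- **Supporting model.** Data Analysis also plans a multivariable regression "after adjustment for age, sex, BMI, and anesthesia type".
- **Population.** Section 2 sets an upper age limit of 18 and no lower age, weight or height limit.
- **Allocation.** Randomization Process balances on sex and surgery type only.
- **Target difference.** The sample size paragraph in section 2 says of 250 mL: "This effect size has been used in the total hip literature, and it is considered to be a clinically significant difference in blood loss".
- **Data available.** Section 3 lists "Patient height (cm) and weight (kg) at time of admission" among the items recorded. Apart from the EBV formula and BMI, no planned analysis uses them.

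**The concern.** Two children with the same proportional fall in hematocrit get very different scores in mL if one is much larger. Part of the between-patient spread in the endpoint is therefore body size, which the treatment cannot affect and which is known before surgery. An unadjusted t-test leaves that spread in the error term.

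Three things are at stake:

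- **Precision.** The trial plans 12 evaluable patients per arm, so removable variance matters.
- **Chance imbalance.** Size is not a balancing factor. In a sample this small, one arm can end up with larger patients, which would partly imitate or mask a drug effect in the primary comparison.
- **Meaning of the target.** A difference of 250 mL, carried over from total hip surgery, is a much larger share of a small child's blood volume than of an adolescent's.

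**Working it through.** **1. The plan's own figure.** Inputs from section D: "Effect size or change expected between groups: 250cc", planning SD 233.69 mL (mean 671.24 mL, so CV = 233.69/671.24 = 0.348), 12 per arm, "Alpha level: 0.05", "Beta or power level: 0.81". Data Analysis adds "All hypotheses will be evaluated with two-sided tests".

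- SE of the arm difference = 233.69 × √(2/12) = 95.4 mL. Noncentrality = 250/95.4 = 2.62 on 22 degrees of freedom.
- Two-sided 0.05: power 70.7%. One-sided 0.05: power 81.4%.

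The stated 81% is reproduced only by a one-sided test. That is a separate matter. The baseline used below is 71%, under the plan's two-sided rule.

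**2. How the formula scales with size.** The documents give no heights or weights, so the sizes are assumed. EBV in litres:

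- Boys, 1.10 m/18 kg: 0.3669 × 1.331 + 0.03219 × 18 + 0.6041 = 1.67
- Boys, 1.70 m/60 kg: 0.3669 × 4.913 + 0.03219 × 60 + 0.6041 = 4.34
- Girls, 1.10 m/18 kg: 0.3561 × 1.331 + 0.03308 × 18 + 0.1833 = 1.25
- Girls, 1.70 m/60 kg: 0.3561 × 4.913 + 0.03308 × 60 + 0.1833 = 3.92

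Ratios: 4.34/1.67 = 2.6 (boys) and 3.92/1.25 = 3.1 (girls). A hematocrit fall of 0.10 gives a red-cell loss of 167 against 434 mL (boys) and 125 against 392 mL (girls). As a share of EBV, 250 mL is 15% (boys) or 20% (girls) at the smaller size, and about 6% at the larger.

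**3. What the supporting regression captures.** BMI alone separates sizes poorly in children: 14 kg/0.95 m has BMI 15.5 and 30 kg/1.35 m has BMI 16.5, while the plan's EBV rises 1.8-fold (boys) or 2.2-fold (girls). But age and sex are in the same model. In simulations with assumed growth curves (ages 5-12 or 4-18):

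- BMI alone explained about 15-43% of EBV variance. Age, sex and BMI together explained about 60-91%.
- For ages 5-12, with the total spread scaled to the planning SD, age, sex and BMI explained 44-45% of the variance in mL. EBV itself explained 54-75%.

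**4. Size of a chance imbalance.** Let R² be the share of the planning variance that size explains. A one-standard-error imbalance in size shifts the arm difference by √R² × 95.4 mL.

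- R² = 0.2: 0.447 × 95.4 = 43 mL (17% of 250 mL)
- R² = 0.5: 0.707 × 95.4 = 67 mL (27% of 250 mL)

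**5. Power after adjustment.** Residual SD = 233.69 × √(1 − R²); two-sided t-test, difference 250 mL, lost degrees of freedom ignored.

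| Assumed R² | Residual SD (mL) | Power, 12 per arm | Power, 15 per arm |
|---|---|---|---|
| 0 | 233.7 | 71% | 81% |
| 0.2 | 209.0 | 80% | 88% |
| 0.3 | 195.5 | 85% | 92% |
| 0.5 | 165.2 | 94% | 98% |

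Taking off three degrees of freedom (EBV, sex and surgery type; 19 instead of 22 at 12 per arm) changes the 12-per-arm figures for R² of 0.2, 0.3 and 0.5 to 79%, 84% and 94%.

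**The case against.** The case for leaving the plan alone is that randomisation protects the comparison, the regression already handles size, and the planning SD already contains it. Much of this stands, and it rules out several stronger readings.

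- **A reader might infer that BMI is the only allowance for size.** It is not. Age and sex are in the same regression, and age is a strong proxy for size in children. What remains is that this model is not the primary analysis, and that it uses BMI where weight or EBV would be more direct.
- **A reader might infer bias.** The documents do not support that. Allocation does not depend on size, so any imbalance is due to chance.
- **A reader might infer that the sample size is wrong for this reason.** If the 24 earlier cases had a similar mix of sizes, SD 233.69 already includes size variation. The point is an unused gain, not an error in the calculation.
- **A reader might put the imbalance higher.** A weight SD of 8-15 kg at 25 mL/kg would give a one-standard-error shift of about 82-153 mL. It would also imply an SD from weight alone of 200-375 mL, which is 73-258% of the planning variance. The whole standard error of the arm difference is only 95 mL, so such figures conflict with the plan.
- **A reader might conclude that mL/kg should be the primary endpoint.** That is a debatable change of endpoint, and the plan's formula does not give constant blood volume per kg. At the assumed sizes it gives 93 against 72 mL/kg for boys and 70 against 65 for girls.

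It is also true that the transfusion term has no EBV factor, so the proportionality applies to the red-cell-loss term and not to the whole endpoint in transfused patients.

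**Conclusion.** The point holds as a missed gain in precision and a problem of interpretation. The primary t-test makes no allowance for body size, the plan's formula ties red-cell loss to EBV, and neither eligibility nor allocation restrains size. At 12 per arm, a one-standard-error size imbalance is worth about 43-67 mL, and adjustment would lift two-sided power from 71% to about 80-94%.

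Both ranges rest on an assumed R² of 0.2 to 0.5. The documents give no distribution of body size, so the true value is unknown. They also take SD 233.69 as applying to the primary endpoint, although section D gives it for intra-operative loss. The direction of the effect follows from the formula; its size does not.

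**What to change.** 1. Make the primary comparison a prespecified linear model of calculated blood loss in mL on treatment, with baseline EBV (or weight) and the minimisation factors sex and surgery type as covariates. State what becomes of the Mann-Whitney fallback; it could stay as an unadjusted sensitivity analysis.
2. In the supporting regression, replace BMI with EBV or weight.
3. Report loss as a percentage of EBV as a supportive analysis. Express the 250 mL target on that scale too, using the 24 existing cases.

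**Cost.** A change of SAP wording, re-expression of the 24 cases, and slightly more analysis. The model spends one degree of freedom on EBV and one each on sex and surgery type, which takes at most about one percentage point off the power figures above. Height and weight are already collected, so no new trial data are needed. The endpoint stays in mL, so comparison with the hip literature is kept.

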All tests and imaging used in this study are considered standard of care.

Randomization Process:

The patients will be randomized into one of 2 groups: (1) Loading dose and infusion of EACA (2) Equivalent volume of normal saline prepared by the pharmacy. An EACA loading dose of 100 mg/kg with a max of 4-5 grams will be given up to 1 hour prior to incision. During the case, an EACA infusion of 33 mg/kg/hr (max of 1 gram/hr) will be maintained. The use of EACA will be terminated at the end of the case. Assignment of patients will be made based on a sequential treatment assignment or minimization strategy in order to ensure an even distribution of patients in each treatment arm. More specifically, each patient will be randomized to the treatment arm that would minimize differences between groups. Randomization will be stratified by sex and surgery type (bilateral VRO, bilateral VRO with associated soft tissue or osseous procedure) so that the number of male/female patients and VRO/associated procedure patients will be balanced in each study group between trial arms.

The Biostatistics Core of the HSS Healthcare Research Institute will randomize each patient based on the minimization strategy. It will be a double-blind experiment with all parties, except the pharmacy, anesthesiologist, and designated research assistant, being blinded to the randomization schedule (surgeon, medical staff, and patient). Patient recruitment will continue until a total of 30 patients are enrolled.

Treatment Groups:

Bilateral VROs will be performed as per the study surgeon's routine practice. In general, the operative extremity will be prepped and draped in the usual sterile fashion. Prior to incision, the anesthesiologist, will administer a loading dose of 100 mg/kg of EACA with (max of 4-5 grams) or an equivalent volume of normal saline prepared by the pharmacy. The loading dose may be give up to 1 hour prior to incision. During the case, an EACA infusion of 33 mg/kg/hr (max of 1 gram/hr) will be maintained. Only anesthesiologists agreeing to participate in the study will be paired with the study surgeons, and all anesthesiologists will be aware of a patient's randomization to the treatment or placebo group.

Outcome Measures

Primary outcome: Calculated total blood loss.

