Secondary outcomes of interest: Postoperative transfusion requirements (allogeneic blood transfusion and intraoperative cell saver utilization), post-operative blood loss, length of stay, and post-operative complications.

Calculated total blood loss will be determined from the difference between the preoperative hemoglobin and the postoperative hemoglobin (or the lowest postoperative hemoglobin during the hospital stay prior to transfusion). Based on hemoglobin balance, the estimated blood loss will be calculated according to the formula by Nadler et al.¹⁷:

```
Estimated Blood Volume (EBV) = (k_1 \text{ x Height}^3 \text{ (m)}) + (k_2 \text{ x Weight (kg)}) + k_3
For men, k_1 = 0.3669, k_2 = 0.03219, and k_3 = 0.6041
For women, k_1 = 0.3561, k_2 = 0.03308, and k_3 = 0.1833
```

Multiplying the EBV by the hematocrit (Hct) gives the red blood cell (RBC) volume. As such, a change in the RBC volume can be calculated from a change in the Hct level^{23,24}:

```
Total RBC volume loss = EBV x (Hct Preop – Hct Postop)
```

Transfusions (mean volume per unit at HSS, 250 mL) can be taken into account by calculating the total blood loss¹⁶:

Total blood loss (L) = Total RBC volume loss + (No. of Units Transfused x 0.25) / (Hct Preop – Hct Postop) / 2)

The rate of perioperative blood transfusions, both intraoperative and postoperative, will be documented for analysis.

The criteria for transfusion of blood products will be a hemoglobin level of < 7.0 g/dL or a hemoglobin level of < 10.0 g/dL with clinical signs of symptomatic anemia (e.g., unexplained tachycardia, hypotension unresponsive to fluids or vasopressors, change in mental status, low

urine ouput, and shortness of breath). Blood will be administered 1 unit at a time, and the presence of symptoms or signs will be reassessed after each unit. This algorithm may be altered by the treating physician (e.g., PACU attending, surgeon, or the OR anesthesiologist), however all decisions will be supported by reasonable documentation. Drains will be removed on POD 2 unless specified by the attending surgeon. Of note, the chart of the patient will clearly indicate him/her as a study patient.

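### Allocation is minimised on sex and surgery type, but the primary test uses neither and the supporting regression omits surgery type; if these factors predict blood loss, power is forgone

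*Combined protocol and SAP*

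**What the plan says.** Under Randomization Process, patients are assigned by a minimisation strategy and "Randomization will be stratified by sex and surgery type (bilateral VRO, bilateral VRO with associated soft tissue or osseous procedure"). Under Data Analysis, the primary outcome is to be "compared between the EACA and placebo groups with a two-sample t-test". The Sample Size section adds a "non-parametric Mann-Whitney U test if assumption of normality is not met". Data Analysis also plans multivariable linear regression, as a further analysis, "after adjustment for age, sex, BMI, and anesthesia type". Sex is in that list and surgery type is not. No section provides a stratified test, a test adjusted for the minimisation factors, or a re-randomisation test. The data lists in section 3 itemise sex, height and weight but not surgery type.

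Sex also enters the outcome itself. The blood-volume formula under Outcome Measures, repeated under Data Analysis, has separate constants: "For men, k_1 = 0.3669, k_2 = 0.03219, and k_3 = 0.6041" and "For women, k_1 = 0.3561, k_2 = 0.03308, and k_3 = 0.1833".

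**The concern.** Balancing the arms on a factor that predicts the outcome removes that factor's contribution to the chance difference between arms. A t-test that ignores the factor still counts its variance as error. The estimate stays unbiased, but the standard error is too wide, the true type I error falls below 5%, and the precision gained by balancing is not used. With 24 to 30 patients, a few points of power matter. As planned, surgery type shapes the allocation and then appears in no analysis.

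**Working it through.** **Inputs from the documents.** Difference 250 mL; SD 233.69 mL and mean 671.24 mL (Sample Size: "the mean calculated intra-operative blood loss was 671.24mL (SD: 233.69"); two-sided 0.05; 12 per arm needed, 30 enrolled (section 2: "Expecting that 10-25% of patients will be excluded").

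**Baseline.** The standard error of the difference at 12 per arm is 233.69 × √(2/12) = 95.4 mL. Exact two-sided t-test power is 70.7%, not the stated 81%. A one-sided test gives 81.4%, and 15 per arm two-sided gives 80.7%. That gap is a separate sample-size matter; about 70% is simply the baseline here.

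**Why the standard error is too wide.** Let R² be the share of within-arm variance explained by the two factors. With perfect balance, the true standard error is 95.4 × √(1 − R²). At R² = 0.22 this is 95.4 × 0.883 = 84.3 mL. In simulation, with 6 of 30 patients lost at random, the t-test reported 95.3 mL on average against a true 87.3 mL.

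**R² for sex.** At equal height and weight, the constants give a boy 0.418 to 0.422 L more estimated blood volume (EBV) than a girl; for example, 1.946 against 1.526 L at an assumed 1.2 m and 22 kg. With an assumed 50:50 sex split and equal hematocrit fall, R² = (half the sex difference / 233.69)². The total-blood-loss equation has unbalanced parentheses, so the sex difference depends on the reading:

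- Red-cell term as printed, EBV × fall. Assumed falls of 0.10, 0.15 and 0.20 give 0.42 L × fall = 42, 63 and 84 mL, so R² = 0.008, 0.018 and 0.032.
- The same term divided by an assumed mean hematocrit of 0.30. Falls of 0.10 and 0.15 give 140 and 210 mL, so R² = 0.09 and 0.20.
- Pilot mean scaled in proportion to blood volume. Assumed sizes of 1.0 m/15 kg, 1.2 m/22 kg, 1.5 m/40 kg and 1.7 m/60 kg give 226, 162, 97 and 68 mL, so R² = 0.23, 0.12, 0.04 and 0.02.

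**R² for surgery type.** The documents give neither the association nor the split. As an illustration, an assumed 150 mL difference gives 150² × p(1 − p) / 233.69² = 0.10, 0.066 and 0.037 at splits of 50:50, 80:20 and 90:10.

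**Power.** Simulation: deterministic minimisation of 30 patients, 24 analysed, normal errors, 50:50 splits, 40,000 trials per case.

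| Prognostic factor(s) | R² | t-test | Model with sex + surgery type | Change (points) |
|---|---|---|---|---|
| Neither | 0 | 70.3% | 68.7% | −1.6 |
| Sex | 0.04 | 70.3% | 70.3% | 0.0 |
| Surgery type | 0.06 | 70.5% | 71.3% | +0.8 |
| Surgery type | 0.10 | 70.6% | 73.2% | +2.6 |
| Sex | 0.12 | 70.8% | 74.1% | +3.3 |
| Sex 0.12 + surgery type 0.10 | 0.22 | 71.3% | 79.1% | +7.8 |
| Sex | 0.23 | 71.4% | 79.6% | +8.2 |
| Surgery type | 0.25 | 71.7% | 80.7% | +9.0 |

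A separate simulation of three of these cases gave 69.9% against 68.8% (neither), 70.8% against 74.3% (sex 0.12) and 71.4% against 78.7% (0.12 + 0.10). If all 30 are analysed, the corresponding figures are 80.8% against 80.2%, 81.9% against 85.1%, and 83.1% against 88.9%.

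**Type I error.** In the 40,000-trial runs the t-test's error is 4.7%, 4.1% and 3.2% at sex R² of 0.04, 0.12 and 0.23, and 3.3% at 0.12 + 0.10. The model's is 5.0%. A further simulation allocated and analysed 24 patients, with a 0.8 chance of the balancing arm and 6,000 trials. At R² = 0.3 the t-test's error was 2.3% under minimisation but 4.9% under simple 1:1 allocation, so the conservatism comes from balancing and then ignoring the factors. At R² = 0.2, power was 71.6% for the t-test, 67.4% for Mann-Whitney, 74.9% for a model with sex alone and 78.7% with both factors.

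**The case against.** An unadjusted t-test that is unbiased and does not inflate type I error is a legitimate primary analysis, and a sex-adjusted regression is already planned. The case for adjustment also leans on assumed inputs. On the red-cell term as printed, sex explains at most about 0.03 of the variance, below break-even. At sex R² 0.012 alone, power is 70.6% for the t-test against 69.3% adjusted. The largest sex figure requires a pilot of very small children: 671 mL would be 54% of the average estimated volume (1.245 L) at 1.0 m and 15 kg. The equal hematocrit fall that creates the sex effect has no support in the documents. If few patients have VRO alone, surgery type offers little: the 150 mL difference by itself changes power by +0.7 points at 80:20 and −0.4 at 90:10.

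All of this stands as a limit on size. A reader might infer from the sex-specific constants that the documents themselves establish a large sex effect, and so a large loss of power. They do not: the constants fix the difference in blood volume, but its share of the outcome variance runs from about 0.01 to 0.23 depending on the reading of the equation, body size and hematocrit fall.

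The objection does not remove the mismatch. The regression is supplementary and lacks surgery type, so the primary test still ignores both factors. The stakes are also uneven: at most about 2 points lost, against about 3 to 9 gained at R² of 0.12 to 0.25.

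**Conclusion.** The point holds as one of efficiency. Allocation uses sex and surgery type, the primary test and its fallback use neither, and no planned analysis uses surgery type. With 24 of 30 analysed, adjusting for both factors costs about 1 to 2 points of power if neither is prognostic. It breaks even at a combined R² of about 0.04, and gains about 3 points at 0.12 and 7 to 9 at 0.20 to 0.25. These figures assume normal errors, losses at random and mostly 50:50 splits. Where the trial will fall in that range cannot be read from the documents.

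Two stronger inferences are not supported. The t-test is not invalid: its type I error falls below 5% rather than rising above it, and its power stays at about 70% in every 24-patient case above. Nor does this mismatch explain the gap between the stated 81% and the recomputed 70.7%, which is present with no covariates at all.

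**What to change.** Make the primary analysis a pre-specified linear model of calculated total blood loss on treatment, sex and surgery type, with both factors taken from the randomisation record. Report the adjusted difference with its 95% confidence interval. If normality fails, use either a re-randomisation test that replays the minimisation or a rank test stratified by the two factors. The first needs the arrival order and the exact algorithm, including any random element, to be on record. The second has up to four strata, on average 24 / 4 = 6 patients each. Keep the unadjusted t-test as supportive, and add surgery type to the supporting regression.

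The cost is analysis-plan wording and one data item that must already be known in order to allocate. If neither factor is prognostic, the price is about 1 to 2 points of power with 24 analysed, or 0.5 to 0.7 with all 30.

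### No planned analysis adjusts for preoperative hematocrit or hemoglobin, although the primary outcome is built from it and it is already collected; prespecifying it is a cheap improvement of modest and uncertain size

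*Combined protocol and SAP*

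**What the plan says.** Outcome Measures (section 3), repeated under Data Analysis (section D), defines the primary outcome: "Calculated total blood loss will be determined from the difference between the preoperative hemoglobin and the postoperative hemoglobin". The accompanying formulas multiply an estimated blood volume, built from height and weight, by the preoperative-minus-postoperative hematocrit, and add a transfusion term.

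Under Data Analysis the outcome is "compared between the EACA and placebo groups with a two-sample t-test", with a Mann-Whitney fallback given under Sample Size. Regression models are also planned, "after adjustment for age, sex, BMI, and anesthesia type". Continuous secondary outcomes, including allogeneic transfusion, are analysed in the same way as the primary one.

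The minimization (Randomization Process, section 3) balances sex and surgery type. The list of items taken from the electronic medical record includes "Preoperative CBC data and coagulation study data". The baseline value will therefore be in hand, but it is neither a covariate nor a balancing factor.

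Transfusion criteria are absolute hemoglobin levels (below 7.0 g/dL, or below 10.0 g/dL with clinical signs), which the treating physician may alter with documentation.

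**The concern.** A fall from baseline is usually correlated with the baseline itself: a patient who starts high has further to fall, and part of a high starting value is measurement noise. With about 12 patients per arm and no balancing on hematocrit, the arms can easily differ on it by chance. If blood loss depends on starting hematocrit, some of that imbalance appears in the estimated treatment difference. A baseline covariate that predicts the outcome also reduces residual variance.

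For transfusion the link is more direct. The criteria are absolute levels, so a child who starts with a low hemoglobin reaches them after a smaller loss.

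The sponsor already accepts covariate adjustment in principle. The gap is one covariate, and it is the one built into the outcome.

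**Working it through.** **Inputs from the plan.** Section D, Sample Size: "Alpha level: 0.05"; "Beta or power level: 0.81"; "Effect size or change expected between groups: 250cc"; SD 233.69 mL and mean 671.24 mL from 24 earlier cases; 12 per arm. Data Analysis: "All hypotheses will be evaluated with two-sided tests with statistical significance set at" 0.05.

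**The plan's own power figure.** Noncentral-t power for 250 mL, SD 233.69 and 12 per arm is 70.7% two-sided and 81.4% one-sided. The stated 81% is reproduced only one-sided. That is a separate issue; 70.7% is the reference here because the plan says two-sided.

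**Assumptions, not in the documents.** Preoperative and lowest postoperative hematocrit have means a = 38 and b = 27 and SD 3 points each; their correlation ρ is 0.3 to 0.7; blood volume V is 2,000 mL; whole-blood loss = V × (pre − post) / [(pre + post)/2].

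**Scale check.** 2,000 × 11 / 32.5 = 677 mL, close to the sponsor's 671.24 mL. Red-cell loss alone would be 2,000 × 0.11 = 220 mL, less than the 250 mL target difference. The whole-blood scale is therefore the relevant one.

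**Slope of loss on preoperative hematocrit.** To first order, with equal SDs, slope = 4V(b − ρa)/(a + b)² = 8,000 × (27 − 38ρ)/4,225 mL per point. Simulation agrees and also gives the outcome SD, so that R² = (slope × 3 / SD)².

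| ρ | First-order slope | Simulated slope | Simulated SD (mL) | R² |
|---|---|---|---|---|
| 0.3 | 29.5 | 29.6 | 226 | 15% |
| 0.5 | 15.1 | 15.1 | 194 | 5% |
| 0.7 | 0.8 | 0.5 | 156 | 0% |

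The first-order slope is zero at ρ = 27/38 = 0.71 and negative beyond that.

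**Varying blood volume.** With a 20% coefficient of variation in V (a further assumption), the outcome SD is 210 to 268 mL, which brackets the sponsor's 233.69. R² falls to about 0% to 11%, and the slope is essentially unchanged.

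**Effect of an imbalance.** The SE of the arm difference in preoperative hematocrit is 3 × √(2/12) = 1.22 points, and 1.96 × 1.22 = 2.4 points. Multiplied by 0, 15 and 30 mL per point, this gives 0, 36 and 72 mL, or 0% to 29% of 250 mL.

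**Power with adjustment.** Residual SD = 233.69 × √(1 − R²); 24 − 3 = 21 degrees of freedom; variance factor 1 + 1/(24 − 4) = 1.05; two-sided 0.05; 12 per arm.

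| R² | Power |
|---|---|
| 0% | 68.4% |
| 5% | 70.6% |
| 10% | 72.9% |
| 15% | 75.3% |
| t-test, unadjusted | 70.7% |

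Break-even is at r of about 0.23 (R² about 5%). Reaching 81% would need r of about 0.51, outside the range above.

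**Transfusion.** On the mean-hematocrit formula, falling from hemoglobin h to 7.0 g/dL takes a loss of 2(h − 7)/(h + 7) of blood volume: 8/18 = 44% from 11 g/dL and 14/21 = 67% from 14 g/dL. This illustrates the direction only, because 7.0 g/dL is not the sole criterion.

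**The case against.** The case against giving this much weight is substantial, and most of it stands.

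- A reader might infer that the plan is certainly losing power. The documents give no correlation between blood loss and preoperative hematocrit, and under the assumptions used here adjustment ranges from a loss of about 2 points to a gain of about 5.
- A reader might infer that an imbalance passes in full into the result, or that the t-test is biased. Neither is so. It passes through in proportion to the slope, not at all if the slope is zero, and the t-test is unbiased over randomizations. The upper figure of 72 mL needs both a roughly 1-in-20 imbalance and the lowest assumed correlation.
- Larger shares of explained variance, 15% to 35%, can be obtained under the same assumptions, but only for red-cell loss, which does not match the sponsor's mean.
- The printed total-blood-loss formula has unbalanced brackets and divides by half the hematocrit fall. If that divisor applies to the whole sum, an untransfused patient's value is 2 × blood volume and hematocrit cancels. The value of the covariate cannot be judged firmly until this is settled.
- Body size enters the outcome through blood volume and may be the stronger covariate.
- The transfusion contrast is softened by the second criterion and by the physician's discretion.

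None of this removes the omission. It limits its size and the confidence that can be placed in it.

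**Conclusion.** The concern holds as a cheap improvement, with moderate confidence. The omission is plain from the documents; its consequence is not. The 0 to 72 mL shift, and the 68% to 75% power against 70.7%, rest on assumed hematocrit means, SDs and correlations, a blood volume of about 2 L and a mean-hematocrit denominator. Variation in blood volume lowers the explained variance further.

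The main argument for acting is protection against a chance imbalance in a small trial, with the covariate chosen before anyone has seen whether an imbalance occurred. A power gain is possible but not established. Nor should a reader conclude that this adjustment would restore the stated 81% power.

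**What to change.** First correct the printed total-blood-loss formula. Then, before unblinding, amend section D (Sample Size item 1 and Data Analysis):

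1. Make the primary comparison a linear model of calculated total blood loss on arm plus preoperative hematocrit (last blood count before surgery), with any other pre-allocation covariates the sponsor adopts. Report the adjusted difference in mL with its 95% CI and keep the t-test as a sensitivity analysis. At minimum, add preoperative hematocrit to the regression already planned.
2. State the assumed correlation between blood loss and preoperative hematocrit if any power is claimed from the adjustment.
3. Add preoperative hemoglobin as a covariate in the transfusion analysis.

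The cost is a wording change, with no extra patients or measurements. It uses one degree of freedom and loses about 2 points of power (70.7% to 68.4%) if preoperative hematocrit is not prognostic.
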